Statistical Methodology	
Descriptive statistics will be used to summarize the data. Continuous variables will be reported as medians and interquartile ranges or means and standard deviations as appropriate. Categorical variables will be reported as frequencies and percentages. Changes in the scores or times of the ICU Memory Tool®, PROMIS®29 Profile, MOCA-5 minute, Katz and Lawton®, PG-SGA short form®, Five time sit-to-stand and Two-minute step test, from hospital discharge to 3- and 6-month post discharge will be estimated using the Wilcoxon Signed Rank Test (non-parametric alternative to t-test) and compared across different categorical variables (e.g. age, gender, discharged directly to home, 30-day readmission) using ANOVA and continuous variables (e.g. APACHE IV, ICU length of stay) using ANCOVA.
 
A consensus sample would be optimal in this feasibility study (all patients meeting criteria consented and participated), however since that

CONFIDENTIAL: This document is the intellectual property of [name]. Acceptance of this document constitutes the agreement by the recipient that no unpublished information contained herein will be published or disclosed without prior written approval.

	
is unlikely, a convenience sample will be used. The future of patients with COVID-19 disease requiring ICU admission is uncertain. A conservative estimate of 50% of these patients will develop PICS. In the first month at BJH, 29 patients were discharged from the ICU. This translates into approximately 15 patients per month. Although this number may increase or decrease due to uncertainties surrounding the disease. Previous studies (see literature review) suggest care for PICS should begin within 12 weeks of discharge. Therefore once IRB approval is obtained, patients discharged within the past 10 weeks will be screened for possible participation. A post-hoc power analysis will be done.

--	---

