### 2.1 Background and Significance

#### *Background:*

Coronavirus disease 2019 (COVID-19) is a highly contagious virus transmitted via respiratory secretions and was established as a pandemic on March 11, 2020. The severity of the disease ranges from asymptomatic/mild (81%), to severe requiring oxygen (14%) and critical (5%) which requires intensive care unit (ICU) admission, ventilation and life support. Two-thirds of these severe cases will develop the most severe manifestation of the disease, acute respiratory distress syndrome (ARDS). Various epidemiologic reports show that the greatest mortality and morbidity risks concern frail and vulnerable people, in particular the elderly, and patients who suffer from multiple comorbidities or chronic diseases (mainly hypertension, diabetes, cardiovascular disease, chronic, respiratory disease, immune compromised status). Patients requiring a stay in the ICU often have a considerably longer length of stay (LOS) than the typical ICU patient. At Barnes-Jewish Hospital (BJH) the typical LOS for an intubated ICU patient with COVID-19 disease is 10-12 days, whereas a non-COVID-19 medical ICU patient is 3-4 days. Thus far, the greatest attention has been paid to strategies to control contagion diffusion and life-saving measures for these critically ill infected patients. It is now time to focus on the inevitable long-term consequences of surviving COVID-19 disease. This feasibility study will provide information not only regarding the long-term sequelae of COVID-19 disease, but also how to structure future care with a primary emphasis on telehealth, both of which may be important if society is faced with another highly contagious disease.

The patients that survive will likely suffer from secondary physical, cognitive and mental impairments due to their prolonged stay in the ICU. Together, these components comprise the Post Intensive Care Syndrome (PICS). PICS purportedly affects 50 – 70% of ICU survivors which may develop during their stay or after discharge and it is estimated one-third of these survivors will die within a year. Post COVID-19 patients may be at increased risk of PICS due to a prolonged period of respiratory distress and immobility along with the potential of lung fibrosis and cardiovascular

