Day 1-2  Week 10 post initial visit And Week 22 post initial visit	
RC: If patient not enrolled in MyChart or has forgotten how to access, call patient and walk them through obtaining access. Direct link (attached to the patient’s study ID) will be emailed or texted (per patient preference) to access the following surveys, requesting one week turn-around time:
 
ICU Memory Tool® (measures recall and aids in our understanding of quality of life)
 
PROMIS®29 Profile (measures anxiety, depression, fatigue, pain, physical function, sleep and ability to participate in social roles)
 
MOCA-5 minute® (measures cognitive function)
 
PG-SGA short form® (screens for malnutrition risk)

Day 2-9  Week 11 and Week 23 post initial visit	
RC: Will send form email from PI to PCP (if patient agreed to share information) providing an overview of the study (see attached)
 
RC will obtain notice from RedCap when surveys opened. RC will check completeness of survey responses. If surveys not completed within 5 days, send reminder email. If not completed in 7 days, call patient offering to administer surveys over the phone.

Day 11  Week 11 and Week 23 post initial visit	
RC: If patient does not complete surveys within 7 days of receipt and has not responded to phone calls; considered an enrollment fail (start of study) or withdrawal from study (repeat surveys), document on enrollment log.

Day 2-11  Week 11 and Week 23 post initial visit	
RC: If surveys completed, send thank you email. Email and/or call patient to schedule first virtual visit. Email link to research team members for them to review responses in RedCap.

Day 9 – 18  Week 12 and Week 24 post initial visit	
RC: Schedule initial 60-75 minute virtual assessment based on MD schedule. Email all team members to obtain availability in non-physician visit time. Send outlook calendar appointments to team members. All providers engaging in telehealth visits will be licensed in the state where the participant lives.

1-2 days before virtual team visit	
RC: Send reminder email to research team members who will be on the visit. Send agenda for call – member/time slot. Send instructions/link for team members to join the virtual visit. Email the patient the instructions on how to access the virtual appointment in MyChart or the HIPPA approved WashU ZOOM link.

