## **2.4.3 Pre-Study Period**

## **2.4.4 Study Period**

### **Methods:**

## **2.4.6 Observations and Measurements**

### **2.4.6.3 Primary Outcome Measures**

Primary outcomes:

1. Patient adherence and determination of feasibility and acceptance with the virtual clinic and telehealth visits based on the FIM® (feasibility of intervention measure), IAM® (intervention appropriateness measure) and the AIM® (acceptance of intervention measure)
2. Patient attendance record
3. Number of on-time arrivals to the virtual visit
4. Number of patient successfully completed online questionnaires after initial training.
5. Patient primary care or clinic physician feedback using the tools in #1 and open ended comments.

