#### **2.5.2 Premature Discontinuation**

Subjects will be withdrawn if the investigator decides that discontinuation is in the best interest of the subject, inactivity by the subject or the subject requests withdrawal from the study.

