#### **3.2 Sources of Materials**

Review of the patient's electronic medical record (EPIC) may occur anytime between when the patient consents to study conclusion. Responses to surveys will be collected as outlined in the study procedure above.

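### The non-response rule pools death and hospitalisation with disengagement, and adherence and attendance have no stated denominator

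*Combined protocol and SAP*

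**What the plan says.** The rule is in the procedures table of Section 2.4.1, in the row for Day 11, week 11 and week 23. Its trigger has two parts: "If patient does not complete surveys within 7 days of receipt and has not responded to phone calls". A patient who meets both is "considered an enrollment fail (start of study) or withdrawal from study (repeat surveys), document on enrollment log".

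Section 2.5.2 lists the grounds for withdrawal: the investigator's judgement of the subject's interest, and then "inactivity by the subject or the subject requests withdrawal from the study". Neither section has a category for death, hospital admission or inability to respond. Neither has a step to find out why a patient is silent. Section 2.5.1 expects no adverse events and describes no reporting of deaths.

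Section 2.4.6.3 names primary outcome 1 as "Patient adherence and determination of feasibility and acceptance with the virtual clinic and telehealth visits", based on the FIM, IAM and AIM, and primary outcome 2 as "Patient attendance record". Neither there nor in the statistical methods (Section 2.4.6.5) is there a formula, a denominator or a rule for withdrawn patients.

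Three other places bear on the point:
- The background in Section 2.1 says of ICU survivors that "it is estimated one-third of these survivors will die within a year".
- The Synopsis lists readmission as a grouping variable: "discharged directly to home, 30-day readmission) using ANOVA".
- Section 3.2 says that review of the electronic record "may occur anytime between when the patient consents to study conclusion".

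**The concern.** The study asks whether patients are willing and able to use a virtual clinic. Disengagement answers that question; death or a hospital stay does not. If all three carry one code, the withdrawal count cannot be interpreted, and neither can any adherence or attendance rate built on it.

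There is also a loss of data. A patient who is in hospital and cannot be reached at the week 11 check is withdrawn. Nothing says that this patient may return for the week 24 visit or for the FIM, IAM and AIM surveys at weeks 25-26, on which primary outcome 1 rests.

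Finally, the 3- and 6-month symptom changes will describe responders only. Without the number of deaths and admissions beside them, a reader cannot tell how far they represent the group that started.

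**Working it through.** **The plan's own figures.** The plan gives no figure for attrition. Its one derived number is the accrual rate: 29 discharges × 0.50 = 14.5, or about 15 per month, which reproduces. The 80 patients in the Synopsis carry no allowance for loss.

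**Which cases the rule reaches.** The rule applies at three survey rounds only.

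| Patient at the check | Surveys done? | Responds to calls? | Code at Day 11 | Code at week 11 or 23 |
|---|---|---|---|---|
| Lost interest | No | No | Enrollment fail | Withdrawal |
| Died | No | No | Enrollment fail | Withdrawal |
| In hospital, unreachable | No | No | Enrollment fail | Withdrawal |
| In hospital, answers the phone | Either | Yes | Rule not met | Rule not met |

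The first three rows cannot be told apart.

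**How many deaths.** Inputs: N = 80 (Synopsis); last application of the rule at week 23 and final surveys up to week 26 (Section 2.4.1); one-year mortality m. The one-third value of m is the background figure in Section 2.1. The values 10% and 20% are assumptions, and so is a constant hazard from the initial visit.

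Formula: p(w) = 1 − (1 − m)^(w/52); expected deaths = 80 × p(w).

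| m | Week 11 | Week 23 | Week 26 |
|---|---|---|---|
| 10% | 2.2%, 1.8 | 4.6%, 3.6 | 5.1%, 4.1 |
| 20% | 4.6%, 3.7 | 9.4%, 7.5 | 10.6%, 8.4 |
| 1/3 | 8.2%, 6.6 | 16.4%, 13.1 | 18.4%, 14.7 |

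Example: 1 − (2/3)^(26/52) = 1 − 0.816 = 0.184, and 80 × 0.184 = 14.7. The week 23 column is closest to what the rule itself could miscode. Later deaths affect the final surveys.

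**What the missing denominator does.** Suppose, for illustration, that 80% of living patients adhere and that 15 of 80 have died. Then 65 are alive, 0.80 × 65 = 52 adhere and 13 do not.
- All enrolled, deaths counted as failures: 52/80 = 65%.
- Alive only: 52/65 = 80%.
- All withdrawals dropped, if all 13 non-adherers were coded as withdrawn: 52/52 = 100%. This is the extreme case.

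The all-enrolled figure at lower mortality is 0.80 × (1 − 0.051) = 76% at m = 10%, and 0.80 × (1 − 0.106) = 72% at m = 20%. The same data therefore give quite different rates, and the plan does not say which it will report.

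**The case against.** Several stronger readings are tempting, and the documents do not support them.

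- A reader might infer that deaths and readmissions will count as non-adherence. No section says so. With no denominator stated, withdrawn patients might equally be left out.
- A reader might infer that anyone who stops answering is withdrawn. The rule needs both incomplete surveys and no response to calls, and it applies only at the survey rounds. First-round non-responders are enrollment fails. No code is attached to missed touch-base calls, and none to a patient's unanswered final surveys; only the undefined word for inactivity in Section 2.5.2 might reach them.
- A reader might infer that the protocol expects one-third of this cohort to die. The figure is a cited one-year estimate for ICU survivors in general, and follow-up is about six months. The cohort also excludes hospice or comfort care, long-term nursing-facility residents and patients with no plan for independent living (Section 2.3.2). Patients must also pass a phone screen (Section 3.3).
- A reader might turn the one-third figure into a loss of about 9 points of attendance: 7.1 deaths by week 12 plus 13.7 by week 24 gives 20.8 of 3 × 80 = 240 visits, or 8.7%. The arithmetic is right, but it assumes a fixed 240-visit denominator that the plan never states, and that all 80 reach a first visit.

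The best defence is that a death or admission could surface anyway. The coordinator calls at weeks 2 to 10 after the first two visits, team members may contact treating professionals, and the chart stays open to the team. Readmission within 30 days is recorded. The data-collection list is an attachment that is not available here, so it may hold a field for vital status. This stands in part, and it lowers confidence about what will be collected. But none of these routes is a required check, and none changes the code. On its usual definition, counted from hospital discharge, the 30-day window closes before the week 11 check (77 days after the initial visit).

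**Conclusion.** The point holds in limited form. The rule is explicit: followed as written, it pools death and hospitalisation with disengagement and gives a hospitalised patient no stated way back. Because adherence and attendance lack denominators, the pooled cases can push the primary feasibility rates either way, and the direction cannot be known from the plan.

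The size depends on assumptions. Under a constant hazard, the range is about 4 to 15 deaths in 80 by week 26. The upper figure uses a background rate that probably overstates mortality in this selected cohort. Readmissions after 30 days add an amount that the documents do not allow one to estimate. Even 4 cases are worth separating in a sample of 80, since the remedy is cheap. This is a recommended improvement to coding and reporting; it does not show that the feasibility conclusion will be wrong.

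**What to change.** In Section 2.4.1, before a non-responder is coded at Day 11, week 11 or week 23, have the coordinator check EPIC and record one of four states: died; in hospital or facility; alive and not responding; status unknown. Count only alive-and-not-responding as disengagement, and keep status unknown as its own category. Let a hospitalised patient resume at the next survey round. Align the wording on inactivity in Section 2.5.2.

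In Sections 2.4.6.3 and 2.4.6.5, define adherence and attendance per visit and report each on two denominators: all enrolled, and those alive and able to attend. State whether Day 11 enrollment fails belong to the first. Both are needed, because the second alone would hide attrition that matters for a clinic serving a sick population. Show the numbers of deaths and readmissions beside every 3- and 6-month symptom result.

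The cost is a short record check per non-responder, within the chart access that Section 3.2 already allows, and a few sentences of text. The limitation is that deaths outside the health system may be missed and remain as status unknown.

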### **2.3.2 Exclusion Criteria**

1. Severe cognitive deficits or dementia prior to hospitalization
2. Long-term resident of a skilled nursing facility prior to admission
3. Non-English speaking (will not have an interpreter available)
4. Hospice or Comfort Care at discharge
5. No plans to return to some degree of independent living at the time of discharge
6. Pregnant or a prisoner at the time of discharge
7. Blind or deaf

If during the consent process if it is determined the patient will not have a home internet connection or smartphone access for the virtual clinic; or displays the inability to use either a computer or phone for virtual appointments, they will also be excluded from enrollment.

[figure not shown]

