CONFIDENTIAL: This document is the intellectual property of [name]. Acceptance of this document constitutes the agreement by the recipient that no unpublished information contained herein will be published or disclosed without prior written approval.

30 min before each virtual team visit	RC: Email/call patient to address any concerns/questions regarding accessing virtual visit. RC will be “host” of the link for the visit.
Time of virtual team visit	RC: Send text to research team that patient has successfully entered the virtual visit.
During virtual team Visit	RC will function as timekeeper – send “chats or texts” to research team members to keep them on time. Team members will speak one at a time, with other members on mute. MD will start with introduction and overview that summary of recommendations after the visit will be sent to the patient’s PCP and the patient, emphasizing the patient and the PCP will be responsible for implementing and monitoring recommended treatments. Each professional will follow with introduction/any additional questions. The physical therapist and occupational therapist will go last to complete the following if the patient agrees/is able: Katz and Lawton® (measures activities of daily living) Five time sit-to-stand Two minute step test All providers engaging in telehealth visits will be licensed in the state where the participant lives.
1-3 days post virtual team visit	Team Members: responsible for documenting in EPIC their note/summary within 2 days of visit RC: Email patient summary of recommendations are available in MyChart for patient to access. Email PCP that summary is available in MyChart, or fax summary if PCP does not have access to MyChart. Clinic MD may choose to contact PCP personally regarding patient evaluation if they deem necessary.
2, 4, 6, 8, 10 weeks post initial and second virtual team visit	RC: Phone call to patient – What recommendations have been implemented? Any questions for any member of the research team? Any team member: may touch-base with the patient or treating professional (home physical therapist) if recommendations have been implemented by the PCP (e.g. physical therapy, change in medication, change in diet) to determine if they have any questions regarding the treatment initiated. If team member desires a virtual visit with patient – RC will host.

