### **2.4.6.4 Secondary Outcome Measures**

[figure not shown]
Secondary outcomes: (to compare patient characteristics to historical non-COVID-19 patients with PICS)

1. ICU Memory Tool® (measures recall and aids in our understanding of the quality of life)
2. PROMIS®29 Profile (measures anxiety, depression, fatigue, pain, physical function, sleep and ability to participate in social roles),
3. MOCA-5 minute® (measures cognitive function),
4. Katz and Lawton® (measures activities of daily living),
5. PG-SGA short form® (screens for malnutrition risk),
6. Five-time sit-to-stand, and Two-minute step test.

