### **2.4.6.5 Statistical Methods**

Descriptive statistics will be used to summarize the data. Continuous variables will be reported as medians and interquartile ranges or means and standard deviations as appropriate. Categorical variables will be reported as frequencies and percentages. Changes in the scores or times of the ICU Memory Tool®, PROMIS®29 Profile, MOCA-5 minute, Katz and Lawton®, PG-SGA short form®, Five time sit-to-stand and Two-minute step test, from hospital discharge to 3- and 6-month post discharge will be estimated using the Wilcoxon Signed Rank Test (non-parametric alternative to t-test) and compared across different categorical variables (e.g. age, gender, discharged directly to

CONFIDENTIAL: This document is the intellectual property of [name]. Acceptance of this document constitutes the agreement by the recipient that no unpublished information contained herein will be published or disclosed without prior written approval.

home, 30-day readmission) using ANOVA and continuous variables (e.g. APACHE IV, ICU length of stay) using ANCOVA.

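### Sit-to-stand and step tests are done only in patients willing and able, but the visible plan gives inability no value or code and does not say that change results cover only patients tested at both visits

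*Combined protocol and SAP*

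**What the plan says.** Section 2.4.1 (Study Procedures, the row on conduct of the virtual team visit) has one condition that covers three assessments: "The physical therapist and occupational therapist will go last to complete the following if the patient agrees/is able". The list that follows is Katz and Lawton, the five-time sit-to-stand and the two-minute step test.

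Section 2.4.6.4 lists "Five-time sit-to-stand, and Two-minute step test" among the secondary outcomes, whose stated purpose is "to compare patient characteristics to historical non-COVID-19 patients with PICS".

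Section 2.4.6.5, repeated in the Synopsis, says that changes in these scores or times "will be estimated using the Wilcoxon Signed Rank Test (non-parametric alternative to t-test". The changes are then compared across categorical patient factors "using ANOVA and continuous variables (e.g. APACHE IV, ICU length of stay) using ANCOVA".

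The only non-completion rule in the visible text is in section 2.4.1, and it concerns the surveys. Sections 2.4.1 and 3.2.1 refer to data lists in attachments that are not part of the public text.

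**The concern.** The condition joins two different reasons for a missing result. A patient who cannot rise from a chair five times has an outcome, and a poor one. A patient who declines has missing data, although refusal may also reflect fatigue, pain or poor function. The tests come last in a timed visit, so lack of time is a plausible third reason. The visible text does not tell these apart.

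A paired analysis needs two values. The sit-to-stand is a time, so a patient who cannot complete it has none and leaves any comparison that includes that visit. The step test is a count, and inability could be entered as 0, but the plan does not say so.

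Two things are at stake. The summary at each visit describes only those who could do the test. And patients who regain or lose the ability between visits, which is a real change in function, appear nowhere in the change results.

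**Working it through.** **What the text settles.** The plan gives no figure to reproduce: no inability rate, standard deviation, expected change or retention. The only input from the documents is the planned 80 patients (Synopsis). The tests appear only at team visits, so the pairs are initial visit to week 12 and initial visit to week 24. A patient can be in one pair and not the other. Section 2.4.6.5 is present in full and does not say whom the change results cover.

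**What has to be assumed.** Score the first visit as X ~ N(0,1), higher being better. Let follow-up be Y = g + r(ρX + √(1−ρ²)·e), with e ~ N(0,1), where g is the true gain, r the ratio of follow-up to first-visit SD, and ρ the correlation between visits. A patient is unable at a visit if the score is below c = Φ⁻¹(u), where u is the share unable at the first visit. Range shown: u = 5% to 35%, ρ = 0.5 or 0.7, g = 0.30 or 0, r = 0.8, 1.0 or 1.2. All are assumptions.

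**Step 1: level at each visit.** The first-visit median among those able is Φ⁻¹((1+u)/2), against a cohort median of 0.
- u = 5%: Φ⁻¹(0.525) = 0.06.
- u = 35%: Φ⁻¹(0.675) = 0.45.

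At follow-up with g = 0.30 and r = 1, the share unable is p = Φ(c − 0.30) and the excess is Φ⁻¹((1+p)/2).
- u = 5%: p = Φ(−1.645 − 0.30) = 0.026, excess 0.03.
- u = 35%: p = Φ(−0.385 − 0.30) = 0.247, excess 0.31.

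**Step 2: pairs and moves lost** (80 patients, g = 0.30, r = 1.0).

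| Unable at first visit | ρ | Pairs kept | Unable to able | Able to unable | Median change, able at both |
|---|---|---|---|---|---|
| 5% | 0.5 | 74.5 | 3.4 | 1.5 | 0.27 |
| 15% | 0.5 | 63.9 | 8.8 | 4.1 | 0.24 |
| 25% | 0.5 | 53.8 | 13.0 | 6.2 | 0.22 |
| 35% | 0.5 | 44.3 | 16.0 | 7.7 | 0.19 |
| 5% | 0.7 | 74.9 | 3.0 | 1.1 | 0.28 |
| 35% | 0.7 | 46.8 | 13.4 | 5.2 | 0.22 |

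Check on the fourth row: 80 − 44.3 − 16.0 − 7.7 = 12.0 unable at both visits, and 12.0 + 16.0 = 28 = 35% of 80. If only 60 patients reach both visits, multiply by 0.75: 33 to 56 pairs kept.

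**Step 3: direction of bias in the change.** With a true gain of 0.30, the median change among those able at both visits is:
- r = 0.8: 0.08 to 0.26.
- r = 1.0: 0.19 to 0.28.
- r = 1.2: 0.32 to 0.35.

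With no true gain it runs from −0.12 to +0.13. The sign depends on whether spread narrows or widens during recovery, which the documents do not say. The sampling SD of the median change is 0.10 to 0.17. At 5% unable and equal SD the bias is 0.30 − 0.28 = 0.02 to 0.30 − 0.27 = 0.03, which is small. At 35% and r = 0.8 it reaches 0.30 − 0.08 = 0.22, above the sampling SD.

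**Step 4: part of the absence is refusal.** If half of the untested decline at random, 2.5% to 17.5% are unable. The first-visit excess is then Φ⁻¹(0.5125) = 0.03 to Φ⁻¹(0.5875) = 0.22, with 38 to 74 pairs kept.

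**The case against.** The strongest reply is that a code may already exist. The data lists are in attachments that we cannot see. Team members are also "responsible for documenting in EPIC their note/summary within 2 days of visit", and review of the "electronic medical record (EPIC) may occur anytime between when the patient consents to study conclusion", so reasons might be recovered from the notes. This stands as a limit on the recording half of the point, although no visible text requires a note to say why a test was not done. It does not answer the analysis half: section 2.4.6.5 is visible, and a code alone would not say how inability is analysed.

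Second, a signed-rank test obviously uses only patients with two values. That is true, and the planned test is not wrong. What is missing is the label and the count of those left out.

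Third, the rate may be low. The exclusion "No plans to return to some degree of independent living at the time of discharge" and the technology requirement may favour the lower end, where the effect on the change is negligible. This stands. PROMIS-29 physical function, and Katz and Lawton where obtained, also describe function in patients who cannot do the tests.

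Two stronger readings are tempting. A reader might infer that the plan will understate recovery; step 3 shows that the bias can go either way. A reader might also infer that the historical comparison is spoiled. The documents give no historical result for either test and do not say how such series treated inability, so the selection could be similar on both sides. Nor do they support treating refusal as unrelated to function.

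**Conclusion.** The point holds as a minor gap in recording, reporting and definition of the analysis set. On the visible text, inability at either visit removes a patient from the sit-to-stand change analysis, and from the step-test analysis unless it is scored 0. Results among the tested look better than the cohort at each visit whenever some patients are unable and inability goes with poor function. The able/unable moves are lost.

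The size rests wholly on the assumed inability rate, gain, correlation and SD ratio: small at 5% unable, moderate to large at 35%. The direction of bias in the change and any effect on the historical comparison cannot be known from the documents. Katz and Lawton falls under the same condition, so its completeness is also affected, chiefly through refusal. The primary outcomes and PROMIS-29 are not affected.

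**What to change.** **Section 2.4.1.** For each performance test, and for Katz and Lawton, record at each visit: done, unable, declined, or not done for another reason. If the attachment already holds such a field, refer to it. State whether inability on the step test is entered as 0.

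**Section 2.4.6.5.**
1. Report these counts and the able/unable transitions, for each pair of visits, beside the median among those tested.
2. Keep the planned signed-rank and ANOVA/ANCOVA analyses, and state that they apply to patients tested at both visits.
3. Add one pre-specified supportive analysis for the two performance tests, with unable ranked worse than any observed result, for example a sign test. Unable to able counts as better, able to unable as worse, and unable at both as no change, with that number shown. No time has to be invented for an uncompleted sit-to-stand. A signed-rank version would depend on the value chosen: in one scenario (35% unable, r = 0.8, ρ = 0.5, gain 0.30) its power was 53% or 71% according to that value.
4. Leave declined and not-done results missing, count them, and note that refusal may be related to function.
5. In any historical comparison, give the number unable beside the median.

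**Cost.** One four-option field per assessment and visit, a few sentences of text, and one extra test per contrast. The sign test uses direction only, with power of 44% to 79% in the 0.30 SD scenarios, so it supports the planned analysis and does not replace it.
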